#### 6.2.2.7

##### **Physical symptoms**

Cravings will be assessed using a single item from the Mood and Physical Symptoms Scale (MPSS) which evaluates urges to smoke over the last 24 hours on a scale from “0” (Not at all) to “5” (All the time).

6.2.2.8 **Environmental influences**

Level of second-hand smoke exposure will be assessed by evaluating the number of smokers in the household and existence of a household smoking policy using 2 questions from the 2008 National Social Climate Survey of Tobacco Control.

Perceived social support will be assessed using the PROMIS Item Bank Emotional Support 4a Short Form^188 which was developed for the general adult population and which evaluates perceived feelings of being cared for and valued as a person (e.g., “I have someone who will listen to me when I need to talk”) on a 5-point Likert scale ranging from “1” (Never) to “5” (Always).

Perceived provider support will be assessed using the Patient Reported Oncology Provider 5As Delivery, a Yes/No scale asking subjects if their cancer doctor or nurse has delivered any of the 5A’s (i.e., “Advised you to quit smoking cigarettes”) in a recent consult.

6.2.3 Exploratory objectives – implementation outcomes: We will assess patient satisfaction with the proposed virtual treatment delivery modality and intervention content. Patient feedback will be taken into consideration in further refining of intervention protocols, and is important for gathering key information on intervention delivery and potential for implementation in real-world situations.

6.2.3.1 **Acceptability**

Satisfaction with various aspects of the tobacco treatment program will be evaluated through participant survey responses and post-treatment interviews.

6.2.3.1.1 **Surveys**

At the 6-month survey (Supplemental Appendix C), participant satisfaction will be assessed using a mixture of multiple-choice question items: (1) To what extent has the tobacco treatment program met your needs? (2) Did you get the kind of smoking cessation assistance that you wanted; (3) How helpful was the smoking cessation assistance?; (4) How would you rate the quality of the assistance you received? (5) Would you recommend this program?; as well as open-ended free-text items about aspects of the program they found the most/least helpful, challenges faced to participation, and any recommendations for additional topics or programs that would have improved their experience at this time.

	6.2.3.1.2	
Semi-Structured Individual Patient Interviews
 
Following completion of their 6-month follow-up surveys, 40 intervention VIT participants will be randomly selected (based on smoking status) to participate in in-depth exit interviews. Using a semi-structured interview guide, study staff will conduct these virtual interviews. All participants will be asked open-ended questions about a) program engagement: (1) What did you think of the clinician video that you received encouraging you to enroll in the study?, (2) reasons for it being helpful or not; b) counseling: (1) What counseling components/NRT did you find the most helpful? Why?; (2) What counseling components/NRT did you find the least helpful? Why?; c) NRT medication dose and access: (1) Please tell me if you used any NRT medication. How much? How difficult/easy was it to access?; d) logistics and overall impressions: (1) What were some of the challenges you faced to participating?, (2) Probe: virtual assessments, mailed NRT, etc.; e) videoconferencing delivery: (1) Please tell me about your experience connecting with your tobacco counselor via a virtual screen. What did you like about it? Dislike about it? Difficulties to using the program? Benefits to using the program?; and f) cessation advice and assistance received from oncology care team.

6.2.4	Patient Remuneration	
Patient participants will receive \$20 in gift cards for each survey completed (baseline, 3 months, and 6 months; 3 total possible). Subjects who complete a biospecimen sample (saliva or CO breath test) will receive \$40 in gift cards for each sample completed (3mo., and 6mo; 2 total possible). Subjects who are randomly selected for an exit interview will be provided \$20 in gift cards for participation (1 possible). Therefore, subjects have the opportunity to receive up to \$160 in remuneration. (See Supplemental Appendices G-M for Patient Remuneration Letters). The central coordinating site (i.e., MGH) will be responsible for managing the disbursement of gift cards directly to participants.

6.3	NCORP Site Staff Assessments	
At the practice (organizational) level, little is known about the acceptability of integrating tobacco treatment delivery into routine oncology care. In this trial,

Rev. Add4

implementation outcomes will be assessed with mixed methods using qualitative (focus group interviews) and quantitative (surveys) data to be collected from a subset of Site PI, CCDR Leader, and other oncology clinicians and research administrative staff from each participating NCORP site (See Section [3.1](#)). As shown in the NCORP Site Staff Schema (p 7), surveys will be collected at baseline (pre-patient participant enrollment, and then again at approximately 12 and 36 months following baseline).

The NCORP Site Staff assessments will be managed by [name] and her study designated research assistant. The baseline, 12 and 36 month follow-up surveys will be collected using REDCap, (Research Electronic Data Capture), a data management software system supported by the Memorial Sloan Kettering Cancer Center (MSKCC) Information Systems group.

**Staff Survey of Site Characteristics, Organizational Readiness and Perceived Tobacco Treatment Feasibility, Acceptability and Appropriateness:**

As described in Section [3.1](#), the CCDR Leader and site PI from each participating NCORP site will identify a subset of approximately 10 clinicians (nurses, oncologists) and administrative staff (site coordinators, support staff) to provide data about the implementation of tobacco use assessment and treatment. Data collection will include qualitative (focus group interviews) and quantitative (survey) research methods. The baseline site staff surveys will be administered prior to the first site patient enrollment. Post surveys will be conducted approximately 12 and 36 months post the baseline survey. The group interview will be conducted at the 36-month follow-up as well. (See Supplemental Appendices D: Baseline Site Staff Survey, E: 12-month Site Staff Survey, F: 36-month Site Staff Survey).

The content of the mixed methods data collection will focus on several implementation outcomes including Appropriateness, Feasibility, Acceptability, and Sustainability. The focus group interviews will last for approximately 45-60 minutes, and the surveys will require approximately 15 minutes for completion. Site staff participants will be remunerated \$100 incentive in total for completion of each wave of pre- and post-trial surveys (\$20 per survey) and focus group interview (\$40).

**6.3.1 NCORP Site Characteristics:**

At the time of site registration, the CCDR Lead or their designee(s) will complete the site rostering survey. This survey requests that applicable CTEP IDs be grouped into larger practice groups with shared providers, populations served and services offered. For each practice group, the CCDR Lead or their designee(s) will complete items regarding practice characteristics including safety net designation, minority/underserved NCORP status, geographic site location, practice volume, provider mix and ownership, and tobacco cessation services that are available for patients treated at each practice group.

**6.3.2 Organizational Readiness for Implementing Tobacco Use Assessment and Treatment:**

Organizational readiness for the treatment of tobacco use in the context of cancer care and the feasibility of implementing the various

components of the tobacco treatment interventions (EUC and VIT) will be assessed by participating staff pre- and post-trial. Perceptions of site organizational readiness will be measured using the 7-item Organizational Readiness for Implementing Change (ORIC, Shea et al 2014) measure assessing two subscales, change commitment and change efficacy, on a 5-point ordinal scale ranging from 'Agree' to 'Disagree'. A total organizational readiness score, and subscale change commitment and change efficacy score are created.

- 6.3.3 Perceived Tobacco Treatment Feasibility, Acceptability and Appropriateness:
- Staff participants will also rate perceived feasibility, acceptability and appropriateness of the various tobacco treatment interventions being tested in this trial (Weiner et al, 2017) on a 6-point ordinal scale ranging from 'Strongly Disagree' to 'Strongly Agree' Aggregate and intervention-specific summary scores for tobacco treatment feasibility, acceptability and appropriateness are derived. The NCORP Staff Survey will take approximately 20 minutes to complete and will be administered at baseline, defined as after site registration and before the first patient is registered, and at approximately 12 and 36 months after site registration (See Supplemental Appendices D: Site Staff Baseline Survey, E: Site Staff 12-month survey and F: Site Staff 36-month survey).

- 6.3.4 Focus Group Interview
- The focus group interview will assess implementation processes including barriers and facilitators for sustaining tobacco treatment as routine cancer care practice in the NCORP site. The question probes for our implementation-focused focus group interviews will be guided by the Consolidated Framework for Implementation Research (CFIR) and will address the 1) the intervention, 2) inner setting, 3) outer settings, 4) individuals involved, and 5) the process for sustaining tobacco treatment following trial completion.

The focus group interview will be conducted using videoconference software (e.g., Zoom, Doximity, or other HIPPA-compliant platform), enabling audio recording of the focus group interview for subsequent coding of primary implementation themes. The focus group interviews will be scheduled at the convenience of the NCORP staff participants and is expected to take about 45-60 minutes to complete. Focus group interviews will take place at the end of the trial (after patient participant enrollment is closed and 36-month follow-up surveys completed)

Focus group Interviews will be recorded, transcribed and analyzed using NVivo qualitative software. Content analyses will be conducted by the two RAs and overseen by Drs. [name] and [name]. The coders will meet to develop the thematic framework, categories, and coding plan. To ensure coding reliability, coding discrepancies will be resolved through discussion and comparison of raw data. Coding will continue until a high level of reliability (Kappa= >0.80) is established. Drs. [name] and [name] will provide an expert review of the analyses.

Rev. Add4

- 6.3.5 **Monthly Meeting Minutes Data**
- The qualitative and quantitative findings will provide detailed initial data on implementation processes that will inform subsequent testing of multi-level implementation strategies for broad national dissemination into community cancer care settings.
- We will conduct content analysis of monthly meeting minutes with CCDR Leaders and other NCORP site staff to summarize engagement of participating sites. We will explore indicators of engagement (quantity and quality) by documenting the proportion and representativeness of participating stakeholders (Site PIs, CCDR leads, oncology nurses) engaged in monthly meetings, how (approaches used and level of engagement) and when (which parts of the research process) stakeholders engage, and what they did to facilitate integration of tobacco assessment and treatment in cancer care delivery (strategies for identifying current smokers).

Rev. Add3

#### 6.4 Cost

Rev. Add2

We will assess NCORP staff time required to screen all patients for smoking status and identify all current smokers. Each CCDR Leader will fill in costs, including local staff effort (time x base salary) related to eligibility screening. This data will be collected via the weekly Patient Screening Log (Appendix Z2D) All staff time costs will be estimated based on national average wages by job type.

Counseling delivery costs will include the counselor's time, including efforts to contact patients, as well as supervisors' time, all of which will be tracked within study databases.

NRT delivery costs will be estimated using national average retail prices. Overall costs will be standardized per randomized study participant across sites for the cost-effectiveness.

#### 6.5 Treatment fidelity/adaptations

We will collect data about EUC fidelity by asking patients at follow-up whether they were advised to quit by their oncology providers and whether they were referred to the Quitline or other tobacco cessation counseling services. All trial participants will be given a Smokefree Study 2.0 brochure about the NCI Quitline providing instructions to call for tobacco treatment. The MGH Coordinating Center will be responsible for providing and documenting distribution of the Quitline brochure to all Smokefree Study 2.0 Trial participants. The Quitline call center routinely asks participants to identify how they found out about the Quitline. For the duration of this trial, the Quitline will record whether callers identify the Smokefree Study as the source of referral. In addition, the Quitline routinely collects limited demographic information, including caller's telephone number, which will serve as the caller identifier allowing us to link the Quitline database with Smokefree Study 2.0 participants. Twice yearly, the MGH Coordinating Center will send an Excel list of Smokefree Study 2.0 participant study IDs with corresponding telephone numbers to the NCI Quitline Call Center requesting lookback for any caller NCI Quitline contact within the past 6 months. In other words, a data manager from the NCI Quitline Call Center will review the data every 6 months to see if a person who entered the study on Smokefree has also contacted the NCI Quitline. The MGH Coordinating Center will record the

date(s) and duration of Quitline contact into Smokefree Study 2.0 Access database. The NCI Quitline will be listed in the Research Authorization.

For VIT intervention participants, the number of contacts, session content and completion, and NRT dispersal will be documented. For EUC participants, information on the number of quitline sessions and NRT dispensed will be obtained from quitline vendors. MGH research staff will also record the percentage of virtual clinician referral videos (brief videos) opened. Patient engagement will be assessed by documenting dispensal and patient-reported NRT use. All of the treatment fidelity of this data will be monitored by MGH research staff and recorded in an Access database (see MGH protocol).

Following Stirman and colleagues' recommendations (2013), we will track any intervention modifications (e.g., counselor adherence to the VIT manual, medication changes).

#### 6.6 Reach and Adoption

Site coordinators will document the percentage of all current smokers who participate at each site. Using a Patient Screening Log (Appendix Z2D), we will assess the number of eligible patients who were approached and the number of eligible patients who enrolled. Reasons for ineligibility, refusal, and characteristics of refusers, ineligibles, and drop outs will be documented. Consistent with the hybrid effectiveness implementation trial design, we will collect characteristics of ineligibles and refusers to inform future dissemination efforts such that we can evaluate the critical question of whom we are not reaching for tobacco treatment.

The MGH RA will track uptake and utilization on the sites that are engaged in study activities (i.e., participation in monthly calls and patient program enrollment).

## 7. Study Parameters

### 7.1 Patient surveys and samples schedule

Item	Baseline	3 months follow-up	6 months follow-up
Baseline survey (Supplemental Appendix A)	within 30 days of enrollment		
Vital status update		-14 days of target date	
3 month survey (Supplemental Appendix B)		within -7 to +49 days of target date	
3 month sample (saliva) 		within 30 days of 3mo survey completion	
3 month sample (CO) 		within 30 days of 3 mo survey completion	
Vital status update			-14 days of target date
6 month survey (Supplemental Appendix C)			within -7 to +90 days of target date (VIT subjects: must occur after counseling session 11 has a final status)
6 month sample (saliva) 			within 30 days of 6 mo survey completion
6 month sample (CO) 			within 30 days of 6 mo survey completion
Interview			within 90 days of 6 mo survey completion

 Participants who self-report smoking abstinence of at least 7 days at month 3 and/or month 6, on either the survey or during survey outreach, will be requested to provide saliva for cotinine assessments (Section [10.1](#)). Saliva samples will be tested only for cotinine. To avoid false-positives, participants who report use of NRT or e-cigarettes within the last week will be offered the opportunity to instead complete an expired air CO sample (Section [10.2](#))

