### 2.3 Secondary Objectives:

#### 2.3.1 Secondary treatment effectiveness (Aim 1)

Secondary smoking outcomes (5) include:

- Biochemically-verified 7-day point prevalence abstinence at 3-months follow-up
- Self-reported 7-day point prevalence cigarette abstinence at 3- and 6-months follow-up

- Significant reduction (> 50% reduction in reported number of cigarettes per day) in daily smoking from baseline to 3- and baseline to 6-months follow-up
- Continuous (no self-reported smoking since last survey point) and sustained abstinence at 6 months (cotinine-verified at 3-months and 6-months)

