5.6 Duration of Intervention

Patients assigned to Arm B will receive up to 12 weeks of NRT. NRT will be dispensed in 4-week increments.

Patients assigned to Arm B will receive counseling for approximately 6 months.

Patients will receive protocol counseling and NRT (if randomized to Arm B) unless:

- Extraordinary Medical Circumstances: If at any time the constraints of this protocol are detrimental to the patient's health, protocol treatment should be discontinued. In this event submit forms according to the instructions in the EAQ171CD Forms Packet.
- Patient withdraws consent.

Rev. Add3

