#### 11.2.1 Patient Contact Information Form

On the Patient Contact Information Form, patients will be asked for telephone numbers and addresses to facilitate contacting for completion of questionnaires. Patients will be asked if they would like text message reminders of survey availability as well as email reminders. While the default survey administration method will be online, questionnaires will be sent by mail as requested by the patient or

as needed by the study personnel. Administration of questionnaires, both web-based and paper will be coordinated by the OEAU.

Administration of the questionnaires will be triggered based on completion of study milestones marked by submission of forms in RAVE and EASEE-PRO.

Patients will be prompted to complete web-based forms via an email prompt (push notifications or SMS as applicable to the study). These notifications will include a link to the web site for questionnaire completion. Questionnaires will be completed on line using a unique patient account. The web site will reference a toll-free phone number and email address that patients can use to reach the OEAU staff should they have questions or need assistance. All data will be stored on a secure server. Patients who do not complete the web questionnaires within 3 working days of the initial request e-mail will receive up to 3 additional reminders, each 3 days apart. These reminders, like the initial notification, will provide a link to the website for the current surveys, ask the participant to confirm that they have been able to access the web site, and provide both the e-mail address and the toll free help number for support.

If patients still have not responded within 14 days of the original e-mail, the OEAU Research Associate may attempt to telephone the patient and administer the questionnaire over the telephone. The OEAU may send a questionnaire in the mail if the on-line version is not completed. If questionnaires are telephone-administered, they will be marked as such in the database. All surveys, while desired within 3 days of the event, will remain available for participants until either the surveys are completed or they are off-study. Since the completion date is recorded for all surveys, the study team will be able to make relevant determinations for inclusion of this data in specific analyses. However, after telephone follow-up, no additional or extraordinary means will be employed to collect overdue/missing questionnaires.

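### In the VIT arm only, the 6-month survey and its confirming sample wait for counseling session 11; separately, 9.7 scores continuous abstinence with a fixed 3-month look-back that does not follow the survey dates

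*Combined protocol and SAP*

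**What the plan says.** **Survey window.** In 7.1 the 6-month survey falls "within -7 to +90 days of target date (VIT subjects: must occur" after the point at which "counseling session 11 has a final status". The window itself applies to both arms; the session-11 condition applies to VIT alone. Saliva and CO samples are each due "within 30 days of 6 mo survey completion".

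**Time point elsewhere.** Section 2.2.1 places the primary outcome at 6 months after enrollment. Section 5.4 lists the same survey times for both arms, and 11.3 counts them from the baseline survey. None of these has an arm-specific condition. On the length of counseling, 5.6 says: "Patients assigned to Arm B will receive counseling for approximately 6 months".

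**Release and late data.** Section 11.2.1 says: "Administration of the questionnaires will be triggered based on completion of study milestones marked by submission of forms in RAVE and EASEE-PRO". Surveys "will remain available for participants until either the surveys are completed or they are off-study". Because completion dates are recorded, "the study team will be able to make relevant determinations for inclusion of this data in specific analyses".

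**Continuous abstinence.** The definition in 2.3.1 is "Continuous (no self-reported smoking since last survey point". Section 9.7 scores it from one question at the 6-month survey, and a reported gap of 3 months or more since the last cigarette counts as success. Section 7.1 lets the 3-month survey fall anywhere from 7 days before to 49 days after its target.

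**The concern.** Randomization balances the arms at entry. It does not balance an assessment date that in one arm depends on progress through treatment. Progress is unlikely to be neutral: in the preceding trial described in 1.2.1, 57% of the intensive arm had more than 7 sessions, and this was associated with quitting at 6 months. That figure is not a rate of late session 11 here, but it shows why the outcome date should not hang on session status.

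Nothing later in the plan would reveal a timing difference. Section 9.5 looks at dropout and missing data. Section 9.6 compares proportions by chi-square and adjusts only for confounders found to be unbalanced. The GEE model in 9.7 uses the 3- and 6-month data, with no stated use of actual dates. Section 7.1 does not say which condition yields if session 11 has no final status by day +90, and 11.2.1 leaves the inclusion of late surveys to later judgement.

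The scoring rule in 9.7 is a second, separate matter. It departs from 2.3.1 whenever the interval between a patient's two surveys is not 3 months, in either arm. It connects to the first matter because a delayed 6-month survey lengthens that interval.

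**Working it through.** The plan gives no figure on assessment timing to reproduce, and its sample size is not disputed here.

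**1. When does the session-11 condition bind?**

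Inputs: window -7 to +90 days (7.1); session 11 at about week 21 (7.3, headed approximate) or by about week 24 (5.3). Assumption: sessions and survey target share the same day 0. The plan does not give the 6-month target T in days, so three values are shown.

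Let F be the day session 11 gets a final status.
- EUC opens on day T - 7.
- VIT opens on the later of T - 7 and F.
- Delay of opening = max(0, F - (T - 7)).

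| Target T | Window | Session 11 in week 21 (days 141-147) | Session 11 in week 24 (days 162-168) |
|---|---|---|---|
| 182 | 175 to 272 | closes 28-34 days before opening | closes 7-13 days before opening |
| 183 | 176 to 273 | 29-35 days before | 8-14 days before |
| 168 (24 weeks) | 161 to 258 | 14-20 days before | 1-7 days after opening |

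With T at 182 or 183 the condition does not bind for sessions on schedule. It binds on schedule only if the target is 24 weeks and session 11 falls in week 24. A session 11 that closes late enough makes it bind under any target. If the survey target counts from the baseline survey (11.3) and sessions count from randomization, a gap between the two reduces the margin.

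The window is 90 - (-7) = 97 days wide, and the sample may come up to 90 + 30 = 120 days after target. Both limits apply to both arms. They bound the possible shift and are not an estimate of it.

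**2. Continuous abstinence: 9.7 against 2.3.1**

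Assumptions: 3 months = 91 days, 6 months = 182 days. Let S3 and S6 be the survey days. The 2.3.1 definition covers S6 - S3 days; 9.7 covers 91.
- Days uncounted = max(0, S6 - S3 - 91).
- Days demanded beyond the definition = max(0, 91 - (S6 - S3)).

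| 3-month survey | 6-month survey | Interval (days) | Result under 9.7 |
|---|---|---|---|
| day 91 (on target) | day 182 (on target) | 91 | agrees with 2.3.1 |
| day 91 | day 212 (+30) | 121 | 30 uncounted; 91/121 = 75% covered |
| day 91 | day 242 (+60) | 151 | 60 uncounted; 91/151 = 60% covered |
| day 91 | day 272 (+90) | 181 | 90 uncounted; 91/181 = 50% covered |
| day 140 (+49) | day 182 | 42 | demands 49 days too many |
| day 140 | day 212 | 72 | demands 19 days too many |
| day 140 | day 231 (+49) | 91 | agrees with 2.3.1 |
| day 140 | day 242 | 102 | 11 uncounted |
| day 140 | day 272 | 132 | 41 uncounted |

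The error therefore has no single sign. For a fixed S3, each day added to S6 moves the start of the look-back one day later. That either reduces an excess demand or adds an uncounted day. Relative to 2.3.1, delay always shifts the scoring towards abstinence at the margin. A patient who smokes during the delay itself still fails under both rules.

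**The case against.** The strongest case is that the condition has not been shown to do anything. It asks for a final status, not for completion, so a missed or cancelled session might qualify. Session completion is tracked in a coordinating-center database described in another protocol (6.5), which may define the term. On-schedule sessions close before a window based on 182 days opens, and the +90-day limit binds both arms. Assessing after treatment ends is a defensible choice, and this survey also carries the satisfaction items (6.2.3.1.1). EUC patients may answer late too.

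Most of that stands. It limits the point to patients whose session 11 closes late. It does not remove the difference: no rule makes an EUC patient wait, and the endpoint is set by time since enrollment, not by end of treatment. If the satisfaction items are the reason, only they need to wait.

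On continuous abstinence, the parenthesis in 9.7 can be read as treating 3 months as the nominal gap between surveys, in line with 2.3.1. That reading is fair for on-target surveys. It fails once the windows in 7.1 are used, because the scoring threshold stays at 3 months. The mismatch would exist without the session-11 condition.

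A reader might also infer that the continuous-abstinence error always favours abstinence in delayed patients. The documents do not support this: after a 3-month survey at +49 days, a 6-month survey on target or at +30 days makes 9.7 the stricter rule.

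**Conclusion.** Two limited points hold.

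First, 7.1 lets the date of the primary outcome depend on treatment progress in VIT only, against the single time point in 2.2.1, 5.4 and 11.3, and section 9 does not examine timing. With a target of about 182 days and a common day 0, this affects patients whose session 11 closes after about day 175.

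Second, in both arms, the fixed 3-month rule in 9.7 departs from 2.3.1 when survey dates vary. In the examples above it runs from 90 of 181 days uncounted to 49 days demanded in excess, given 91- and 182-day targets.

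A reader might infer that the primary result is biased in favour of VIT, or that VIT patients are assessed up to 97 days late. Neither follows. The documents give no rate of late session 11, and a later date could catch more quits or more relapses. The 97 days is only the window width. No patient count, power loss or direction of bias for the primary outcome can be stated. The case for acting is that the changes are specific and cheap, and remove an arm-dependent rule and a scoring rule that departs from its own definition.

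**What to change.** 1. **Section 7.1.** Release the smoking-status items and the sample request on the same day after one stated anchor (for example Step 2 randomization), with the same window in both arms and independent of session status. If the condition serves the satisfaction items, delay only those. If the condition is kept, at least define final status and say which condition yields at day +90.
2. **Section 9.7.** Score continuous abstinence against the date of the patient's own 3-month survey, as 2.3.1 defines it, as far as the response format allows (the survey forms are in supplemental appendices not reviewed here). Keep the 3-month rule where that survey is missing.
3. **Section 11.2.1 and section 9.** Before data lock, fix one rule, equal in both arms, for including out-of-window surveys and samples. Report days from randomization to survey and to sample by arm. Survey completion dates are already recorded, and the smoking status slips in section 10 carry the sample date.

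If surveys have already been collected under the condition, items 2 and 3 still apply.

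**Cost.** Wording changes in three sections, a changed survey trigger in EASEE-PRO, possibly a separate short satisfaction form for VIT, and one table. Some VIT patients would answer before their last booster session. A mid-trial change creates two timing regimes, so the change date should be recorded and the timing table shown before and after it. The counseling itself does not change.
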